8.4.1.1. Reporting SAEs to Pfizer Safety

All SAEs occurring in a participant during the active collection period as described in Section 8.4.1 are reported to Pfizer Safety using the PSSA immediately upon awareness and under no circumstance should this exceed 24 hours, as indicated in [Appendix 3](#). The investigator will submit any updated SAE data to the sponsor within 24 hours of its being available.

8.4.1.2. Recording Nonserious AEs and SAEs on the CRF

All nonserious AEs and SAEs occurring in a participant during the active collection period, which begins after obtaining informed consent as described in Section 8.4.1, will be recorded on the AE section of the CRF.

The investigator is to record on the CRF all directly observed and all spontaneously reported AEs and SAEs reported by the participant.

As part of ongoing safety reviews conducted by the sponsor, any nonserious AE that is determined by the sponsor to be serious will be reported by the sponsor as an SAE. To assist in the determination of case seriousness, further information may be requested from the investigator to provide clarity and understanding of the event in the context of the clinical study.

Reporting of AEs and SAEs for participants who fail screening are subject to the CRF requirements as described in [Section 5.4](#).

8.4.2. Method of Detecting AEs and SAEs

The method of recording, evaluating, and assessing causality of AEs and SAEs and the procedures for completing and transmitting SAE reports are provided in [Appendix 3](#).

Care will be taken not to introduce bias when detecting AEs and/or SAEs. Open-ended and nonleading verbal questioning of the participant is the preferred method to inquire about AE occurrences.

8.4.3. Follow-Up of AEs and SAEs

After the initial AE or SAE report, the investigator is required to proactively follow each participant at subsequent visits/contacts. For each event, the investigator must pursue and obtain adequate information until resolution, stabilization, the event is otherwise explained, or the participant is lost to follow-up (as defined in [Section 7.3](#)).

In general, follow-up information will include a description of the event in sufficient detail to allow for a complete medical assessment of the case and independent determination of possible causality. Any information relevant to the event, such as concomitant medications and illnesses, must be provided. In the case of a participant death, a summary of available autopsy findings must be submitted as soon as possible to Pfizer Safety.

Further information on follow-up procedures is provided in [Appendix 3](#).

8.4.4. Regulatory Reporting Requirements for SAEs

Prompt notification by the investigator to the sponsor of an SAE is essential so that legal obligations and ethical responsibilities toward the safety of participants and the safety of a study intervention under clinical investigation are met.

The sponsor has a legal responsibility to notify both the local regulatory authority and other regulatory agencies about the safety of a study intervention under clinical investigation. The sponsor will comply with country-specific regulatory requirements relating to safety reporting to the regulatory authority, IRBs/ECs, and investigators.

Investigator safety reports must be prepared for SUSARs according to local regulatory requirements and sponsor policy and forwarded to investigators as necessary.

An investigator who receives SUSARs or other specific safety information (eg, summary or listing of SAEs) from the sponsor will review and then file it along with the SRSD(s) for the study and will notify the IRB/EC, if appropriate according to local requirements.

8.4.5. Environmental Exposure, Exposure During Pregnancy or Breastfeeding, and Occupational Exposure

Environmental exposure occurs when a person not enrolled in the study as a participant receives unplanned direct contact with or exposure to the study intervention. Such exposure may or may not lead to the occurrence of an AE or SAE. Persons at risk for environmental exposure include healthcare providers, family members, and others who may be exposed. An environmental exposure may include EDP, EDB, and occupational exposure.

Any such exposures to the study intervention under study are reportable to Pfizer Safety within 24 hours of investigator awareness.

8.4.5.1. Exposure During Pregnancy

An EDP occurs if:

- A female participant is found to be pregnant while receiving or after discontinuing study intervention.
- A male participant who is receiving or has discontinued study intervention inseminates a female partner.
- A female nonparticipant is found to be pregnant while being exposed or having been exposed to study intervention because of environmental exposure. Below are examples of environmental EDP:
 - A female family member or healthcare provider reports that she is pregnant after having been exposed to the study intervention by ingestion.
 - A male family member or healthcare provider who has been exposed to the study intervention by ingestion then inseminates his female partner prior to or around the time of conception.

The investigator must report EDP to Pfizer Safety within 24 hours of the investigator's awareness, irrespective of whether an SAE has occurred. The initial information submitted should include the anticipated date of delivery (see below for information related to termination of pregnancy).

- If EDP occurs in a participant/participant's partner, the investigator must report this information to Pfizer Safety using the EDP Supplemental Form within PSSA, regardless of whether an SAE has occurred. Details of the pregnancy will be collected after the start of study intervention and until a minimum of 28 calendar days after the last administration of study intervention.

- If EDP occurs in the setting of environmental exposure, the investigator must report information to Pfizer Safety using the PSSA. Since the exposure information does not pertain to the participant enrolled in the study, the information is not recorded on a CRF; however, a copy of the completed PSSA case report form is maintained in the investigator site file.

Follow-up is conducted to obtain general information on the pregnancy and its outcome for all EDP reports with an unknown outcome. The investigator will follow the pregnancy until completion (or until pregnancy termination) and notify Pfizer Safety of the outcome as a follow-up using PSSA. In the case of a live birth, the structural integrity of the neonate can be assessed at the time of birth. In the event of a termination, the reason(s) for termination should be specified and, if clinically possible, the structural integrity of the terminated fetus should be assessed by gross visual inspection (unless preprocedure test findings are conclusive for a congenital anomaly and the findings are reported).

Abnormal pregnancy outcomes are considered SAEs. If the outcome of the pregnancy meets the criteria for an SAE (ie, ectopic pregnancy, spontaneous abortion, intrauterine fetal demise, neonatal death, or congenital anomaly in a live-born baby, a terminated fetus, an intrauterine fetal demise, or a neonatal death), the investigator should follow the procedures for reporting SAEs. Additional information about pregnancy outcomes that are reported to Pfizer Safety as SAEs follows:

- Spontaneous abortion including miscarriage and missed abortion should be reported as an SAE;
- Neonatal deaths that occur within 1 month of birth should be reported, without regard to causality, as SAEs. In addition, infant deaths after 1 month should be reported as SAEs when the investigator assesses the infant death as related or possibly related to exposure to the study intervention.

Additional information regarding the EDP may be requested by the sponsor. Further follow-up of birth outcomes will be handled on a case-by-case basis (eg, follow-up on preterm infants to identify developmental delays). In the case of paternal exposure, the investigator will provide the participant with the Pregnant Partner Release of Information Form to deliver to his partner. The investigator must document in the source documents that the participant was given the Pregnant Partner Release of Information Form to provide to his partner.

8.4.5.2. Exposure During Breastfeeding

An EDB occurs if:

- A female participant is found to be breastfeeding while receiving or after discontinuing study intervention.
- A female nonparticipant is found to be breastfeeding while being exposed or having been exposed to study intervention (ie, environmental exposure). An example of environmental EDB is a female family member or healthcare provider who reports

that she is breastfeeding after having been exposed to the study intervention by ingestion.

The investigator must report EDB to Pfizer Safety within 24 hours of the investigator's awareness, irrespective of whether an SAE has occurred. The information must be reported using the PSSA. When EDB occurs in the setting of environmental exposure, the exposure information does not pertain to the participant enrolled in the study, so the information is not recorded on a CRF. However, a copy of the completed SAE Case Report form from PSSA is maintained in the investigator site file.

An EDB report is not created when a Pfizer drug specifically approved for use in breastfeeding women (eg, vitamins) is administered in accordance with authorized use. However, if the infant experiences an SAE associated with such a drug, the SAE is reported together with the EDB.

8.4.5.3. Occupational Exposure

The investigator must report any instance of occupational exposure to Pfizer Safety within 24 hours of the investigator's awareness using the PSSA, regardless of whether there is an associated SAE. Since the information about the occupational exposure does not pertain to a participant enrolled in the study, the information is not recorded on a CRF; however, a copy of the completed SAE Case Report form from PSSA must be maintained in the investigator site file.

8.4.6. Cardiovascular and Death Events

Not applicable.

8.4.7. Disease-Related Events and/or Disease-Related Outcomes Not Qualifying as AEs or SAEs

Not applicable.

8.4.8. Adverse Events of Special Interest

Not applicable.

8.4.8.1. Lack of Efficacy

The investigator must report signs, symptoms, and/or clinical sequelae resulting from lack of efficacy. Lack of efficacy or failure of expected pharmacological action is reportable to Pfizer Safety **only if associated with an SAE**.

8.4.9. Medical Device Deficiencies

Not applicable.

8.4.10. Medication Errors

Medication errors may result from the administration or consumption of the study intervention by the wrong participant, or at the wrong time, or at the wrong dosage strength.

Medication errors are recorded and reported as follows:

Recorded on the Medication Error Page of the CRF	Recorded on the Adverse Event Page of the CRF	Reported using the PSSA to Pfizer Safety Within 24 Hours of Awareness
All (regardless of whether associated with an AE)	Any AE or SAE associated with the medication error	Only if associated with an SAE

Medication errors include:

- Medication errors involving participant exposure to the study intervention;
- Potential medication errors or uses outside of what is foreseen in the protocol that do or do not involve the study participant.
- The administration of expired study intervention;
- The administration of an incorrect study intervention;
- The administration of an incorrect dosage;
- The administration of study intervention that has undergone temperature excursion from the specified storage range, unless it is determined by the sponsor that the study intervention under question is acceptable for use.
- The administration of study intervention consistent with the medication error descriptions in [Section 6.5](#).

Such medication errors occurring to a study participant are to be captured on the medication error page of the CRF, which is a specific version of the AE page.

Whether or not the medication error is accompanied by an AE, as determined by the investigator, the medication error is recorded on the medication error page of the CRF and, if applicable, any associated AE(s), serious and nonserious, are recorded on the AE page of the CRF.

In the event of a medication dosing error, the sponsor should be notified within 24 hours.

Medication errors should be reported to Pfizer Safety within 24 hours using PSSA **only when associated with an SAE**.

8.5. Pharmacokinetics

Pharmacokinetic parameters are not evaluated in this study.

8.6. Genetics

8.6.1. Specified Genetics

Specified genetic analyses are not evaluated in this study.

8.6.2. Retained Research Samples for Genetics

A 4-mL blood sample optimized for DNA isolation Prep D1 will be collected according to the [SoA](#), as local regulations and IRBs/ECs allow.

Retained Research Samples may be used for research related to the study intervention(s) and COVID-19. Genes and other analytes (eg, proteins, RNA, nondrug metabolites) may be studied using the retained samples.

See [Appendix 5](#) for information regarding genetic research. Details on processes for collection and shipment of these samples can be found in the laboratory manual.

8.7. Biomarkers

Collection of samples for biomarker research is also part of this study.

The following samples for biomarker research are required and will be collected from all participants in this study as specified in the [SoA](#):

- Nasopharyngeal swab will be collected to assess SARS-CoV-2 viral RNA level.
- A plasma sample will be collected to assess SARS-CoV-2 viral RNA level.
- Oropharyngeal swab will be collected to assess SARS-CoV-2 viral RNA level
- A plasma sample will be collected and may be used for protein biomarker analysis.
- Retained research samples.

8.7.1. Viral RNA Assessment (NP Swab)

An NP swab of both nares will be collected by HCP as per the [SoA](#) from participants and will be analyzed to measure SARS-CoV-2 RNA by RT-PCR. At Screening and Baseline (Day 1) only, rapid antigen testing can be done before NP swab collection. At all other timepoints, **NP swab collection must occur prior to any Rapid Antigen Assessment**. Residual samples may be used for viral sequencing to assess for signs of viral evolution and evaluation of potential genetic viral variants, infectivity, phenotypic assays, and additional molecular analysis. Host genetic analysis may also be performed.

Residuals of all samples may be stored for future research. Storage and shipping instructions will be in accordance with the laboratory manual.

8.7.2. Viral RNA Assessment (Plasma)

A 6-mL blood sample will be collected per the [SoA](#) from participants and may be analyzed to measure SARS-CoV-2 RNA by RT-PCR. Residual samples may be utilized for viral sequencing, infectivity and phenotypic assays and additional molecular analysis. Host genetic analysis may also be performed.

Residuals of all samples may be stored for future research. Storage and shipping instructions will be in accordance with the laboratory manual.

8.7.3. Rapid Antigen Assessments

Rapid antigen testing for SARS-CoV-2 will be self-collected by the participant as described in the [SoA](#). Sites will use test kits that are authorized for use in this study. At Screening and Baseline (Day 1) only, rapid antigen testing can be done before NP swab collection. At all other time points, rapid antigen testing must be done after NP swab collection. When participants have 2 consecutive negative rapid antigen tests separated by at least 24[-2]h, rapid antigen testing will revert to on site rapid antigen testing as noted in the [SoA](#).

Site staff should train participants/caregiver at the screening/baseline visit to ensure participants can perform the rapid antigen test appropriately. The participant should perform the baseline rapid antigen testing assessment during the visit to ensure proper sample collection under observation by site staff.

8.7.4. Viral Sequencing Assessments (OP Swab)

An OP swab will be collected by the HCP as per the [SoA](#) from participants may be analyzed to measure SARS-CoV-2 RNA by RT-PCR. **OP swabs should be obtained after NP swab collection and rapid antigen testing.** Residual samples may be utilized for viral sequencing, infectivity and phenotypic assays and additional molecular analysis. Host genetic analysis may also be performed.

Residuals of all samples may be stored for future research. Storage and shipping instructions will be in accordance with the laboratory manual.

8.7.5. Specified Gene Expression (RNA) Research

Specified gene expression (RNA) research is not included in this study.

8.7.6. Specified Protein Research

8.7.6.1. Plasma for Protein Analysis

A 6-mL blood sample will be collected, as specified in the [SoA](#), and isolated for plasma for biomarker analysis. Analysis may include but is not limited to proteomics and immunologic assessments. Residuals of all samples may be stored and used for additional analyses related to COVID-19 and/or the mechanism of action of nirmatrelvir/ritonavir.

Details on processes for collection and shipment of these sample(s) can be found in the laboratory manual.

8.7.7. Specified Metabolomic Research

Specified metabolomic research is not included in this study.

8.7.8. Retained Research Samples for Biomarkers

These Retained Research Samples will be collected in this study:

- 4-mL whole blood Prep B2.5 optimized for serum
- 2.5-mL whole blood Prep R1 optimized for RNA;
- 15-mL urine Prep M3.

Retained Research Samples will be collected as local regulations and IRB/ECs allow according to the [SoA](#).

Retained Research Samples may be used for research related to the study intervention(s) and COVID-19. Genes and other analytes (eg, proteins, RNA, nondrug metabolites) may be studied using the retained samples.

8.8. Immunogenicity Assessments

Immunogenicity assessments are not included in this study.

8.9. Health Economics

Health economics/medical resource utilization and health economics parameters will be evaluated in this study ([Section 8.2.2](#) and [Section 8.2.3](#)).

9. STATISTICAL CONSIDERATIONS

Detailed methodology for summary and statistical analyses of the data collected in this study is outlined here and further detailed in the SAP, which will be maintained by the sponsor. The SAP may modify what is outlined in the protocol where appropriate; however, any major modifications of the primary endpoint definitions or their analyses will also be reflected in a protocol amendment.

9.1. Statistical Hypothesis

The primary hypothesis is to test whether or not there is a difference in mean change of viral RNA level in NP swabs from baseline to Day 5 between nirmatrelvir/ritonavir and the placebo/ritonavir group:

Null hypothesis: $H_0 \quad \mu_{\text{nirmatrelvir/ritonavir}} - \mu_{\text{placebo/ritonavir}} = 0$

Alternative hypothesis: $H_a \quad \mu_{\text{nirmatrelvir/ritonavir}} - \mu_{\text{placebo/ritonavir}} \neq 0$

Where $\mu_{\text{nirmatrelvir/ritonavir}}$ and $\mu_{\text{placebo/ritonavir}}$ are mean change of viral RNA level in NP swabs from baseline to Day 5 for nirmatrelvir/ritonavir and placebo/ritonavir groups.

9.1.1. Estimands

9.1.1.1. Primary Estimand

The primary estimand is the difference in mean change of SARS-CoV-2 RNA level in NP swabs from baseline to Day 5 between nirmatrelvir/ritonavir and placebo/ritonavir group in patients with a rebound in COVID-19 symptoms and a positive rapid antigen test within 2 weeks following completion of an initial 5-day treatment course, who have a positive viral RNA NP swab test result at baseline. This will be estimated without regard to study treatment discontinuation and without regard to prohibited therapies.

9.1.1.2. Secondary Estimands

The secondary estimands are:

- The hazard ratio for time to 2 consecutive negative rapid antigen test results obtained at least 24 (-2) h apart through Day 28 between nirmatrelvir/ritonavir and placebo/ritonavir group in patients with rebound in COVID-19 symptoms and a positive rapid antigen test within 2 weeks following completion of an initial 5-day treatment course, who have a positive viral RNA NP swab test result at baseline. This will be estimated without regard to study treatment discontinuation and without regard to prohibited therapies.
- The hazard ratio for time to sustained alleviation of all targeted signs and symptoms through Day 28 between nirmatrelvir/ritonavir and placebo/ritonavir group in patients with rebound in COVID-19 symptoms and a positive rapid antigen test within 2 weeks following completion of an initial 5-day treatment course, who have a positive viral RNA NP swab test result at baseline. This will be estimated without regard to study treatment discontinuation and without regard to prohibited therapies.

9.1.2. Multiplicity Adjustment

The overall Type I error rate across the primary and key secondary efficacy endpoints will be controlled at alpha = 0.05. Following the positive test of the primary efficacy endpoint in the primary analysis set (mITT), the secondary analysis for the primary efficacy endpoint using the mITT1 analysis set will be tested.

Following the positive test of the secondary analysis, the following secondary efficacy endpoints will be tested using Hochberg method[31]:

- Time to 2 consecutive negative rapid antigen test results obtained at least 24 (-2)h apart through Day 28 in the mITT analysis set.
- Time (days) to sustained alleviation of all targeted signs and symptoms through Day 28 where sustained alleviation is defined as the first of two consecutive days when any symptoms scored as moderate or severe at baseline are scored as mild or absent and any symptoms scored as mild or absent at baseline are scored as absent in the mITT analysis set.

9.2. Analysis Sets

For purposes of analysis, the following analysis sets are defined:

Participant Analysis Set	Description
Full analysis set (FAS)	All participants randomly assigned to study intervention.
Safety analysis set (SAS)	All participants randomly assigned to study intervention and who take at least 1 dose of study intervention. Participants will be analyzed according to the study intervention they received.
mITT	All participants randomly assigned to study intervention who take at least 1 dose of study intervention and who have a positive viral RNA NP swab test result ($\geq 2.0 \log_{10}$ copies/mL) at baseline. Participants will be analyzed according to the study intervention they were randomized.
mITT1	All participants randomly assigned to study intervention who take at least 1 dose of study intervention and who have a positive rapid antigen test result at baseline. Participants will be analyzed according to the study intervention they were randomized.
Per protocol(PP)	All participants in the mITT analysis set without important protocol deviations considered to impact the interpretation of the primary efficacy endpoint. Protocol deviations will be reviewed to generate the list of participants with significant deviations to be excluded from the PP analysis set. The PP exclusion criteria will be finalized prior to breaking the blind.

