	
remains below the LLOQ through Day 34 for participants with NP swab SARS-CoV-2 RNA greater than or equal to the LLOQ at baseline.
 
 Rebound in SARS-CoV-2 RNA level in NP swabs at follow-up (ie, any study visit from Day 10 to through Day 34, defined as a half (0.5) \log_{10} copies/mL increase or greater in SARS-CoV-2 RNA level relative to SARS-CoV-2 RNA level on Day 5 and with a follow-up viral RNA level $\geq 2.5 \log_{10}$ copies/mL. 	

 To compare the effect of nirmatrelvir/ritonavir on the rate of cell culture infectious virus over time in participants with mild-to-moderate COVID-19 	
In participants with detectable viral titers at baseline by TCID50:
 
 Time to negative infectious titer by TCID50. Change in TCID50 from baseline to Days 3, 5, 10, 15, 21, 28, and 34. Proportion of participants with negative infectious titer by TCID50 on Days 3, 5, 10, 15, 21, 28, and 34. 
In participants with positive viral titers at baseline by virus recovery:
 
 Time to negative infectious titer by virus recovery. Proportion of participants with negative infectious titer by virus recovery on Days 3, 5, 10, 15, 21, 28, and 34. 	
 Not applicable

 To compare the effect of nirmatrelvir/ritonavir to placebo/ritonavir on viral concentration in plasma in participants with mild-to-moderate COVID-19. 	
 Change from baseline in SARS-CoV-2 viral RNA level in plasma, over time. 	
 Not applicable.

 To compare the effect of nirmatrelvir/ritonavir to placebo/ritonavir on COVID-19-related hospitalization and all-cause mortality in participants with mild-to-moderate COVID-19. 	
 Proportion of participants with COVID-19-related hospitalization > 24 h or death from any cause through Day 28. 	
 Not applicable.

 To compare the effect of nirmatrelvir/ritonavir to placebo/ritonavir on COVID-19-related healthcare resource utilization in participants with mild-to-moderate COVID-19. 	
 Number of COVID-19-related medical visits through Day 34. 	
 Not applicable.

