9.5. Sample Size Determination

The study will enroll approximately 411 participants.

The sample size calculation is based on the primary efficacy endpoint as the change in viral RNA level from baseline to Day 5 as measured in NP swabs in the mITT analysis set.

Assuming a SD of 1.8 (based on EPIC-HR, NCT04960202), a sample size of approximately

PFIZER CONFIDENTIAL

CT02-GSOP Clinical Protocol Template Phase 1 2 3 4 (14 April 2023)

Page 77

315 evaluable participants (210 participants in nirmatrelvir/ritonavir group and 105 participants in placebo/ritonavir group) is expected to provide 90% power to detect a difference of $0.7 \log_{10}$ copies/mL in viral RNA between groups using a 2-sided 0.05 alpha level test. Assuming approximately 10% of participants will have a negative viral RNA result at baseline, and assuming a non-evaluable rate of 15%, approximately 411 participants will be randomized in the study to achieve approximately 315 participants evaluable for the primary efficacy endpoint.

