6.3.8. Change from Baseline in SARS-CoV-2 Viral RNA Level in Plasma, Over Time

Change from baseline in SARS-CoV-2 viral RNA level in plasma, over time will be analyzed similar to the primary endpoint using MMRM model in mITT analysis set. The LS means and treatment difference for each visit will be calculated and presented with their corresponding 95% CIs.

6.3.9. Proportion of Participants with COVID-19-related Hospitalization >24h or Death from Any Cause through Day 28

The number and proportion of participants with COVID-19-related hospitalization >24h or death from any cause through Day 28 will be summarized by treatment group. The analyses will be done using the mITT analysis set.

6.3.10. Number of COVID-19-related Medical Visits through Day 34

Number of COVID-19-related medical visits through Day 34 will be summarized by treatment group descriptively (n, mean, standard deviation, median, min, max). The analysis will be done using the mITT analysis set.

6.3.11. Time (days) to Sustained Resolution of All Targeted Signs and Symptoms through Day 28

Sustained resolution of all targeted COVID-19 signs/symptoms is defined as the event occurring on the first of 2 consecutive days when all targeted COVID-19 symptoms are scored as absent. The first day of the 2 consecutive-day period will be considered the First Event Date.

For symptoms with no reported severity in baseline, the symptom will have to be absent in order to be counted as sustained resolution (missing severity at baseline will be treated as mild).

Day 27 is the last possible day that symptom resolution can be achieved (definition includes data from the subsequent day) and Day 28 is the last day participants report their daily signs and symptoms.

The time to sustained symptom resolution for the purpose of this study is defined as:

- For a participant with sustained symptom resolution, time to event will be calculated as (First Event Date) – (First Dose Date) +1.
- For a participant that either completes Day 28 of the study or discontinues from the study before Day 28 without sustained symptom resolution (censored), censoring date will be at the last date on which symptom resolution is assessed, and time will be calculated as (Censoring Date) – (First Dose Date) +1 or Day 27 whichever occurs first.

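### Hospitalization or death and COVID-19 medical visits are summarised only in the RNA-positive mITT, although neither needs a baseline RNA value; adding mITT1 would be a cheap, minor improvement

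*Protocol*

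**What the plan says.** Protocol 9.2 and SAP section 4 define the mITT as randomised participants "who take at least 1 dose of study intervention and who have a positive viral RNA NP swab test result" at baseline, with a threshold of 2.0 log10 copies/mL. The mITT1 has no RNA condition. It takes randomised participants "who take at least 1 dose of study intervention and who have a positive rapid antigen test result at baseline".

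The Protocol (9.3.4) leaves the tertiary analyses to the SAP, so the operative text is there:

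- SAP 6.3.9: "The number and proportion of participants with COVID-19-related hospitalization >24h or death from any cause through Day 28 will be summarized by treatment group", and then "The analyses will be done using the mITT analysis set".
- SAP 6.3.10: "Number of COVID-19-related medical visits through Day 34 will be summarized by treatment group descriptively", again with the mITT as the only set named.
- SAP Appendix 1 lists mITT alone for both endpoints. For sustained symptom resolution, which is also exploratory, it lists mITT and mITT1.

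SAP section 4 adds in general terms that mITT1 serves the efficacy endpoints for which it is relevant. The specific sections and Appendix 1 do not assign it to these two.

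**The concern.** The reason recorded for the RNA condition, in the Amendment 3 entry of Protocol Appendix 12, is that the primary endpoint is a change in RNA and so needs a quantifiable baseline. That reason does not reach a proportion of participants hospitalized or dead, or a count of medical visits. Both are plain descriptive summaries with no RNA term. A randomised, dosed participant whose baseline swab is negative or missing drops out of both tables whatever happens later.

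Hospitalization and death are likely to be rare here, so each event matters to a by-arm count. The plan is also uneven. mITT1 was added for the primary endpoint, both efficacy secondary endpoints and symptom resolution, but not for these two clinical outcomes, and no reason is given. What is at stake is the completeness of two exploratory tables.

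**Working it through.** **Inputs.** From Protocol 9.5 and SAP 2.4: SD 1.8, difference 0.7 log10 copies/mL, two-sided alpha 0.05, 90% power, 315 evaluable (210 + 105), 15% non-evaluable, 411 randomised, and "Assuming approximately 10% of participants will have a negative viral RNA result at baseline". From Protocol 4.1: 2:1 allocation.

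1. **Reproduce the plan's sample size.** Placebo n = (1 + 1/2) × (1.960 + 1.282)² × 1.8² / 0.7² = 1.5 × 10.51 × 6.61 = 104.2, so 105. With 210 active this gives 315, as stated. Inflation: 315 / (0.90 × 0.85) = 411.8, against 411 stated. The figures agree. The 10% is thus a loss of RNA-negative participants separate from the 15% non-evaluable.

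2. **Participants left out.** 0.10 × 411 = 41.1, or about 27 active (41.1 × 2/3) and 14 placebo (41.1 × 1/3). The mITT keeps about 370 (247 + 123) of 411 (274 + 137), taking all randomised participants as dosed. The 10% is a planning value. Over an assumed range of 5% to 20%, the number left out is 21 to 82. Participants with a missing baseline swab would come on top.

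3. **Chance that at least one event is left out.** Let K be the total number of hospitalization-or-death events among all dosed participants, and p the share outside the mITT. If RNA-negative participants carry the same risk as the rest (assumed; the documents give no figure), the chance is 1 − (1 − p)^K and the expected number omitted is pK.

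| K | p = 5% | p = 10% | p = 20% | Expected omitted at 10% |
|---|---|---|---|---|
| 2 | 10% | 19% | 36% | 0.2 |
| 4 | 19% | 34% | 59% | 0.4 |

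   K is not given in the documents and may be zero. The retrospective review in Protocol 2.1 describes 4 rebound cases, all mild and none hospitalized.

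4. **Precision if no placebo event is seen.** The 95% upper bound by the rule of three is 3/123 = 2.4% in the mITT against 3/137 = 2.2% in all dosed participants.

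5. **Where else the events would appear.** Death and inpatient hospitalization are SAE criteria (Protocol 10.3.2), and SAP 6.2.3 summarises SAEs in the Safety Analysis Set, which has no RNA condition. Two gaps remain. Protocol 10.3.1 does not count expected progression of the disease under study as an AE unless it is more severe than expected, so a COVID-19 hospitalization may not always be recorded as an SAE. And the visit types listed in Protocol 8.2.2, such as urgent care, practitioner's office and telemedicine, are counted in no safety table.

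**The case against.** The best defence is that this is a declared choice. SAP section 4 names the mITT as the primary efficacy set, and the RNA condition is written into both secondary estimands, although antigen clearance and symptom alleviation need no baseline RNA value either. One efficacy population throughout is coherent, and both endpoints here are exploratory, with no estimand. This stands as a reason to keep the mITT rows. It does not explain why symptom resolution gets mITT1 and these two endpoints do not.

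Several stronger readings are tempting, and the documents do not support them:

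- **That the objective contradicts the analysis set.** Protocol section 3 speaks of "COVID-19-related hospitalization and all-cause mortality in participants with mild-to-moderate COVID-19" with no RNA condition. But the primary and symptom objectives use the same population phrase while their estimands require a positive baseline RNA result, so the phrase does not fix an analysis population.
- **That the comparison is biased.** Membership depends on a baseline swab, taken at the latest within 1 hour after the start of dosing (SAP 3.4), so randomisation still protects the contrast between arms.
- **That about 10% of events are lost.** The 10% is a planning share of participants, not of events.
- **That a loss is likely.** The first-course rates in Protocol 2.2.1 would give 137 × 0.0631 + 274 × 0.0087 = 11.0 events, and 1 − 0.9^11 = 69%. Those rates come from untreated acute infection, not from rebound after a completed course, and should not be used to size this point.
- **That the fix would bring the table into line with the safety tables.** The counts would still differ. The endpoint is COVID-19-related care over 24 hours, or any death, through Day 28, while the SAE criterion is admission for any cause. SAP section 4 also removes some participants from the efficacy analyses for GCP issues, an exclusion that it does not apply to safety.

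**Conclusion.** The point holds as a minor matter of completeness. The RNA restriction serves no purpose in these two summaries and leaves about 41 of 411 participants out of them on the protocol's own 10% assumption. The expected loss of hospitalization-or-death events is well below one if the trial has 2 to 4 in all, with a 19% to 34% chance of missing at least one under equal risk, and the gain in precision is slight. Medical visits lose more, because non-serious visits by the excluded participants are summarised nowhere else.

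A reader might infer that deaths vanish from the trial report or that error control is affected. Neither follows. Deaths and most hospitalizations remain visible as SAEs, and both endpoints lie outside the testing hierarchy of Protocol 9.1.2, so alpha and power are untouched.

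**What to change.** In SAP 6.3.9, 6.3.10 and the two matching rows of Appendix 1, report both endpoints also in mITT1, beside the mITT result. All randomised and dosed participants would serve equally well. Since a positive rapid antigen test is an entry criterion, the two wider sets should nearly coincide.

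The cost is one extra population in two descriptive tables. No new data are needed, because the schedule of activities has medical visits recorded at follow-up visits through Day 34 without reference to the RNA result.
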